6.2.2 Preoperative Eligibility

Once written informed consent has been obtained, the Preoperative Eligibility CRF will be completed to document adherence to the preoperative inclusion and exclusion criteria from Section 5.5.

Where a subject fails to fulfill any element of the preoperative eligibility criteria, this will be documented and any signed consent form and completed preoperative inclusion/exclusion criteria retained by the Principal Investigator. The subject will not be advanced any further into this clinical investigation.

6.2.3 Subject Identification

After a subject has signed informed consent and/or met the preoperative inclusion and exclusion criteria, the subject will be allocated to the next available investigation number (subject ID number).

The subject ID number will consist of the site number and the subject number. The subject number will be 01 for the first subject, 02 for the second subject and so on. This subject ID number will be the unique identifier of the subject and included on each CRF page and all other investigational documentation relating to that subject.

6.3 Preoperative Procedures and Evaluations

The following data will be collected and recorded at the preoperative visit on the Preoperative CRF:

- Demographic data;
 - Age,
 - Gender,
 - Race and ethnicity,
- Physical exam and laboratory tests;
 - Height,
 - Weight,
 - Diastolic and systolic blood pressure,
 - CBC (Laboratory CRF),
 - Coagulation status (Laboratory CRF),
 - Chemistry panel (Laboratory CRF),
 - Pregnancy test for females of child-bearing age (Laboratory CRF),
 - Blood draw for antibody testing,
- Medical history; and
 - Coagulation disorder(s),

- History of bleeding requiring hospitalization in the last five years,
- Disease process / indication for surgery,
- Concomitant illnesses,
- Surgical history related to the surgical area,
- Diabetes,
- Smoking history,
- Malignancies and prior therapies,
- Hepatic disease,
- Concomitant medications potentially impacting coagulation status (Concomitant Medication CRF).

The Laboratory CRF will be completed and applicable concomitant medications will be recorded on the Concomitant Medication CRF. A blood draw for antibody testing will be performed and handled per specified procedures agreed upon with the investigational site and core laboratory.

6.4 Intraoperative Procedures and Evaluations

All subjects will undergo the same intraoperative investigational evaluations. Intraoperative is defined as the time interval from when the subject enters the surgical suite until the subject exits the surgical suite.

Subjects undergoing the open elective cardiothoracic, abdominal, and orthopedic lower extremity surgeries are eligible for enrollment into the clinical investigation. The Investigator will perform the surgery per his or her standard procedures, including conventional methods of hemostasis (pressure, ligation, cautery, etc.).

6.4.1 Intraoperative Inclusion Criteria

A subject must then meet all of the following intraoperative inclusion criteria:

- Subject does not have an active or suspected infection at the surgical site;
- Subject undergoing cardiothoracic surgery with anticoagulation must have anticoagulation reversed prior to TBS identification and treatment;
- Subject in whom the Investigator is able to identify a TBS for which any applicable conventional means for hemostasis are ineffective or impractical; and
- Subject has a TBS with an SBSS score of 1, 2, or 3.

If all of these intraoperative eligibility criteria are met, then the subject is formally randomized and enrolled into the clinical investigation (unless the subject is a lead-in subject; all lead-in subjects will receive HEMOBLAST™).

6.4.2 Randomization and Hemostat Application

At the start of each surgical procedure, a single HEMOBLAST™ device and a single G+T device will both be prepared per the respective Instructions for Use (unless the subject is a lead-in subject; all lead-in subjects will have a single HEMOBLAST™ device prepared). The preparation time for both devices will be recorded for the TTH Population subjects.

Randomization will be performed through sequentially numbered sealed envelopes. Four-hundred subjects (TTH Population) will be randomized to receive HEMOBLAST™ or G+T in a 2:1 ratio:

- 267 subjects will be randomized to receive HEMOBLAST™; and
- 133 subjects will be randomized to receive G+T.

There will be a maximum of 50 lead-in subjects; these subjects will not be randomized. The first subject for each investigator will be treated as a lead-in subject. These subjects will receive HEMOBLAST™ and will be followed for safety only (maximum Full Analysis Population of 450); lead-in subjects will not count towards the TTH Population. Please see Section 12 below for additional detail on subject populations.

Randomization will be stratified by surgical indication and will incorporate blocking; additional details of randomization and blocking will be included in a separate Randomization Plan.

After randomization and enrollment, the assigned hemostat will be used in the investigational subject; the other hemostat will be discarded following institutional procedures.

A study-specific stopwatch will be used to track hemostat application and the times of hemostasis evaluation. The time of initial hemostat application will be considered time 0; at this time, the stopwatch will be started by the study coordinator. The stopwatch will run continuously without stopping.

Hemostasis will be evaluated by the investigator at the following time points until hemostasis has been achieved:

- 3 minutes;
- 6 minutes; and
- 10 minutes.

Reapplication of the randomized hemostat will be performed at the 3 minute and 6 minute evaluation time points, as described below.

For cardiothoracic procedures, the TBS will be identified after heparin reversal. Additionally, the TBS will not be at the site of a valve implant or at the site of a synthetic graft or patch implant.

HEMOBLAST™ will be applied according to its instructions for use.

1. Peel open the pouches to remove contents with attention to sterile procedures.
2. Remove cap using a twisting motion.
3. Blot excess blood from the target bleeding site with gauze/pad or suction so the hemostatic implant material may be applied directly to the source of bleeding. The wound surface should be as dry as possible before application.
4. Apply hemostatic implant material to the source of bleeding by squeezing the bellows. Enough implant material should be applied to cover the entire source of bleeding.
5. Immediately use a wet laparotomy pad to hold the hemostatic material at the target bleeding site using wound appropriate pressure to conform the powder to the source of bleeding.
6. Maintain the hemostatic material at the target bleeding for approximately three minutes. Gently lift the laparotomy pad and inspect the area.
7. If hemostasis has not been achieved, repeat steps 3-6 or use an alternate method of hemostasis treatment.
8. Discard any unused product after opening.

HEMOBLAST™ contraindications include:

- Do not inject directly into the blood vessels.
- Do not apply HEMOBLAST™ Bellows in the absence of active blood flow, e.g., while the vessel is clamped or bypassed. Extensive intravascular clotting and even death may result.
- Do not use HEMOBLAST™ Bellows for treatment of severe or brisk bleeding.
- Do not administer to patients with known allergies or hypersensitivity to materials of porcine or bovine origin.
- To avoid risk of allergic-anaphylactoid reaction and/or thromboembolic events, which may be life-threatening, do not inject HEMOBLAST™ Bellows into a vessel or tissue.
- Do not use in the closure of skin incisions because it may interfere with the healing of the skin edges due to mechanical interposition of the powder.

After randomization, G+T will be applied to the TBS per the Instructions for Use for subjects assigned to this treatment group.

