12.3.2.2 Methods of Analysis

Summaries of the number and percent of subjects with at least one SAE will be provided. Comparisons of the proportion of subjects experiencing SAEs will be made between treatment arms. Summaries of the number of percent of AEs will be provided for each treatment arm.

Differences in mean overall blood loss, mean volume of intra-operative transfusions, mean total operative time, and mean duration of hospitalization will be estimated using linear regression models with stratified adjustment for surgery type and separated by surgery type. In all cases, the robust variance estimator will be used and a 95% Wald-based interval will be computed. Comparisons of the incidence of re-operation (total and reoperation due to bleeding) and the incidence post-surgery bleeding complications will be made using a general linear model to estimate the difference in the probability of each outcome after stratified adjustment for surgery type. Comparisons of the incidence of re-operation and the incidence post-surgery bleeding complications within each surgery type will be made using a two sample binomial test of proportions.

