The trial will utilize a 2:1 randomization scheme (HEMOBLAST™ : G+T). Randomization will be stratified by surgery indication and it is anticipated that accrual to each surgical indication will be roughly equal. It is envisioned that one interim analysis will be performed during the monitoring of the study, occurring after outcomes have been observed for 240 randomized and treated subjects belonging to the TTH Population (approximately 160 subjects treated with HEMOBLAST™ under 2:1 randomization), and may continue to a maximal sample size of 400 subjects (approximately 267 subjects treated with HEMOBLAST™ under 2:1 randomization). Although the above interim analysis is pre-defined, final inference for comparable efficacy will treat the futility boundary as non-binding (implying that the type I error rate for the trial will be bounded at or below .025 even if the futility boundary is crossed at the interim analysis but the trial continues on).

Under such a monitoring schedule and assuming a probability of TTH within 6 minutes of 88% in both the HEMOBLAST™ arm and the G+T arm, a maximal sample size of 400 treated subjects (267 in the HEMOBLAST™ arm and 133 in the G+T arm) will provide approximately 80.1% power to determine comparable efficacy based upon a 10% non-inferiority margin of absolute difference in the probability of TTH within 6 minutes. Of particular note, if the study were to stop in favor of comparable efficacy at the interim analysis after 60% of the maximal sample size were accrued, data would be available on approximately 160 patients in the TTH Population treated with HEMOBLAST™ plus up to an additional 50 lead-in subjects. Assuming equal accrual to each surgical indication this would provide safety data on roughly 70 subjects treated with HEMOBLAST™ for each surgery type.

Enrollment will continue in parallel with the interim analysis. Thus, if the interim analysis supports early termination of the clinical investigation, the number of subjects included may be higher than the number available at the time of the interim analysis. All available data for the analysis populations defined above will be included in the final analysis and report.

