8.2 Randomization

At the start of each surgical procedure, a single HEMOBLAST™ device and a single G+T device will both be prepared per the respective Instructions for Use (unless the subject is a lead-in subject; all lead-in subjects will have a single HEMOBLAST™ device prepared). The preparation time for both devices will be recorded for the TTH Population subjects.

Randomization will be performed just prior to treatment through sequentially numbered sealed envelopes. Four-hundred subjects (TTH Population) will be randomized to receive HEMOBLAST™ or G+T in a 2:1 ratio:

- 267 subjects will be randomized to receive HEMOBLAST™; and
- 133 subjects will be randomized to receive G+T.

There will be a maximum of 50 lead-in subjects; these subjects will not be randomized. The first subject for each investigator will be treated as a lead-in subject. These subjects will receive HEMOBLAST™ and will be followed for safety only (maximum Full Analysis Population of 450); lead-in subjects will not count towards the TTH Population. Please see Section 12 below for additional detail on subject populations.

Randomization will be stratified by site and will incorporate random permuted blocking; additional details of randomization and blocking will be included in a separate Randomization Plan.

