10.6.2 Analytic Methods

Endpoints used to characterize the safety profile include the rate of occurrence of all AEs and SAEs, reoperation rate due to bleeding, mean volume of intraoperative transfusions, total operative time, mean

duration of hospitalization, intraoperative blood product administration, and post-operative blood product administration.

Summaries of the number and percent of subjects with at least one SAE will be provided. Comparisons of the proportion of subjects experiencing SAEs will be made between treatment arms. Summaries of the number of percent of AEs will also be provided for each treatment arm.

Differences in mean overall blood loss, mean volume of intra-operative transfusions, mean total operative time, and mean duration of hospitalization will be estimated using linear regression models with stratified adjustment for surgery type and separated by surgery type. In all cases, the robust variance estimator will be used and a 95% Wald-based interval will be computed. Comparisons of the incidence of re-operation (total and reoperation due to bleeding) and the incidence post-surgery bleeding complications will be made using a general linear model to estimate the difference in the probability of each outcome after stratified adjustment for surgery type. Comparisons of the incidence of re-operation and the incidence post-surgery bleeding complications within each surgery type will be made using an exact two sample binomial test of proportions.

For binary endpoints, the proportion and corresponding 95% scored-based confidence interval will be computed. The proportion of UADEs or SADEs will also be computed and a 95% scored-based confidence interval will be computed for the true UADE or SADE rate. In the event that no UADEs or SADEs are observed, the upper bound of the 95% confidence interval will be based upon the exact binomial distribution.

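### The between-arm SAE comparison has no stated adjustment for surgical indication, although randomisation is stratified by it and the modelled safety comparisons beside it are adjusted

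*Protocol*

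**What the plan says.** **Randomisation.** Protocol 6.4.2: "Randomization will be stratified by surgical indication and will incorporate blocking". Protocol 12.4.1 repeats this: "Randomization will be stratified by surgery indication and it is anticipated that accrual to each surgical indication will be roughly equal". SAP 10.7.1 carries the same sentence. SAP 8.2 differs: "Randomization will be stratified by site and will incorporate random permuted blocking".

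**SAE comparison.** Protocol 12.3.2.2, with the same sentence in SAP 10.6.2: "Comparisons of the proportion of subjects experiencing SAEs will be made between treatment arms". No test, model, interval or adjustment is given.

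**Neighbouring safety comparisons.** Blood loss, transfusion volume, operative time and hospital stay are "estimated using linear regression models with stratified adjustment for surgery type and separated by surgery type". Reoperation and post-surgery bleeding complications, which are binary like SAEs, are compared "using a general linear model to estimate the difference in the probability of each outcome after stratified adjustment for surgery type".

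**Intervals.** SAP 10.6.2 adds: "For binary endpoints, the proportion and corresponding 95% scored-based confidence interval will be computed". That is an interval for a single proportion, not for a difference between arms.

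**Population.** Protocol 12.3.2.1 and SAP 10.6.1 analyse safety in the Full Analysis Population, meaning all randomised and treated subjects plus all lead-ins. Under Protocol 6.4.2 there are at most 50 lead-ins. Each is an investigator's first subject, is not randomised, and receives HEMOBLAST.

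**Status.** Protocol 12.2.4 and SAP 10.10 class any comparison outside the fixed testing sequence as exploratory. SAEs are outside it.

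**The concern.** SAE risk plausibly differs between cardiothoracic, abdominal and orthopedic lower extremity surgery. After randomisation blocked within indication, a crude comparison still counts between-indication variation as noise, although the design has removed it from the contrast. The standard error is then too large and the test runs below its nominal level. For a safety outcome that is the unhelpful direction, because an excess of harm becomes harder to see.

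The lead-ins raise a second issue. Their surgery mix follows the specialties of the enrolling investigators, and all of them are on one arm. Nothing balances that mix against the control arm, so a crude contrast in the Full Analysis Population can show a difference in surgery mix as if it were a device effect.

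**Working it through.** **The plan's own figure.** None is given for the SAE comparison. The stated 80.1% power belongs to the primary endpoint. It reproduces (80.0% with the futility boundary obeyed, 81.4% with it ignored) and has no bearing here.

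**Inputs from the documents.** 267 HEMOBLAST and 133 G+T subjects (Protocol 6.4.2); roughly equal accrual to three indications (Protocol 12.4.1), so 267/3 = 89 and 133/3 = 44.3 per indication; up to 50 lead-ins, all HEMOBLAST.

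**Assumed.** SAE rates by surgery type and the surgery mix of the lead-ins. Neither is in the documents. No device effect is assumed.

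**Step 1: precision among randomised subjects.** Let r_s be the SAE rate in indication s and r the mean of the three.

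- Crude variance = r(1 − r) × (1/267 + 1/133)
- Stratified variance = mean of r_s(1 − r_s) × (1/267 + 1/133)
- 1/267 + 1/133 = 0.01126

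Worked case, rates 30/20/5%: r = 18.33%.

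- Crude: √(0.1497 × 0.01126) = 4.11 points
- Stratified: mean of 0.21, 0.16 and 0.0475 = 0.1392; √(0.1392 × 0.01126) = 3.96 points
- Ratio: 1.037

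| Assumed rates (%) | Crude SE ÷ stratified SE |
|---|---|
| 10/10/10 | 1.000 |
| 20/15/10 | 1.007 |
| 15/10/5 | 1.009 |
| 20/10/5 | 1.019 |
| 30/20/5 | 1.037 |
| 30/10/5 | 1.049 |
| 40/25/5 | 1.063 |
| 40/15/5 | 1.076 |

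**Step 2: size of a crude nominal 5% test.** Size = 2 × [1 − Φ(1.96 × SE ratio)]. At 30/20/5% this is about 4.2%, and at 40/25/5% about 3.7%. Simulation with 2:1 permuted blocks of 6 within indication (an assumed block size) gave 4.5% and 4.0%. These figures apply only if randomisation is blocked within indication.

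**Step 3: bias among randomised subjects.** With both arms balanced within indication, the crude difference has expectation zero in every scenario.

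**Step 4: bias from lead-ins.** With l_s lead-ins in indication s, the HEMOBLAST group has 267 + 50 = 317 subjects and the crude difference shifts by Σ l_s(r_s − r) / 317.

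| Lead-in split (highest to lowest risk) | Assumed rates (%) | Shift (points) |
|---|---|---|
| even | any | 0 |
| 25/15/10 | 15/10/5 | (25×5 + 15×0 − 10×5)/317 = +0.24 |
| 25/15/10 | 40/15/5 | (25×20 − 15×5 − 10×15)/317 = +0.87 |
| 30/10/10 | 30/20/5 | +0.74 |
| 30/10/10 | 40/25/5 | +1.05 |
| 50/0/0 | 15/10/5 | 50×5/317 = +0.79 |
| 50/0/0 | 40/15/5 | 50×20/317 = +3.15 |

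The sign reverses if lead-ins lean towards the low-risk surgery: a 10/15/25 split at 15/10/5% gives −0.24.

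**Step 5: if SAP 8.2 is what is implemented.** Balance by indication is then not guaranteed. Approximating this by simple 267:133 permutation, chance imbalance adds error with mean zero and standard deviation of about 0.4 points (15/10/5%) to 1.2 points (30/10/5%).

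**The case against.** The strongest reply is that the documents are silent here rather than wrong. No crude method is named, so an analyst could adjust the SAE comparison and still comply. That is correct, and the efficiency figures apply only if the sentence is taken at face value. But nothing in the plan requires adjustment, while reoperation, also binary, has it spelled out a few lines later.

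A reader might go further and infer three things that the documents do not support.

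- **That the SAE confidence interval is too wide.** No interval for the SAE difference is planned. The SAP's score intervals are for single proportions.
- **That the SAE comparison is confounded by surgery type.** Under the protocol's scheme, stratified randomisation prevents this among randomised subjects. Only the lead-ins open a route, and no lead-in surgery mix is given.
- **That SAEs are the one exception.** Overall AEs and blood product administration also lack a between-arm method, which points to thin specification rather than a single misjudged analysis.

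It is also fair to say that the comparison is exploratory, carries no power target or success criterion, and will be accompanied by safety results presented by surgery type (Protocol 12.2.3, SAP 10.9). That presentation would make a mix difference visible, but it supplies no adjusted contrast. Finally, the lead-in shift is small against sampling error: 1.05 points beside a crude standard error of 4.49 is 0.23 standard errors.

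**Conclusion.** The point holds as a modest improvement to an exploratory safety contrast. The factor that the protocol uses to stratify randomisation, and that the plan uses to adjust its modelled safety comparisons, is not carried into the SAE comparison.

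Read as crude, that comparison loses 0 to 8% in standard error and errs on the conservative side. The lead-in bias is zero to about 1 point in the even and moderately uneven cases worked, and about 3 points only if every lead-in falls in the highest-risk surgery type with rates as far apart as 40/15/5%. All of these sizes rest on assumed SAE rates and lead-in mixes. The efficiency and test-size figures also need randomisation stratified by indication, which SAP 8.2 contradicts.

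Stratifying would remove only the surgery-mix part of the lead-in problem. Other differences, such as being each investigator's first case, would remain, which is why the main contrast belongs in randomised subjects. Overall study success (Protocol 12.1.4) is unaffected.

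**What to change.** 1. In Protocol 12.3.2.2 and SAP 10.6.2, define the between-arm SAE contrast as a risk difference with Cochran-Mantel-Haenszel weights by surgical indication, the weighting already used for the primary endpoint (Protocol 12.3.1.2), with a stratified 95% confidence interval, computed in randomised and treated subjects.
2. Report SAEs in lead-ins separately. Give the Full Analysis Population contrast, also stratified by indication, as a sensitivity analysis. Keep crude percentages as description.
3. Reconcile SAP 8.2 (stratified by site) with Protocol 6.4.2, Protocol 12.4.1 and SAP 10.7.1 (stratified by indication), so that the analysis follows the scheme actually used.

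The cost is a few sentences in each document, with no new data and no additional subjects. It should be settled before the comparative safety data are seen.

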6.4.3 Bleeding Severity and Hemostasis Evaluations

Bleeding severity and hemostasis will be assessed using the SBSS.

An SBSS score will be assigned at the following time points until hemostasis is achieved:

- Baseline – when evaluating intraoperative eligibility;
- 3 minutes;
- 6 minutes; and
- 10 minutes.

An SBSS score of 0 is equivalent to hemostasis. All other SBSS scores are considered failure of hemostasis. See below in Table 6.

Table 6. Bleeding Severity and Hemostasis

SBSS Score	0	1	2	3	4	5
Verbal Descriptor	None	Minimal	Mild	Moderate	Severe; not immediately life-threatening	Extreme; immediately life-threatening
Visual Descriptor	Dry	Oozing	Pooling	Flowing	Streaming	Gushing
Expected Intervention(s)	None	Manual pressure, cautery, adjuvant hemostat(s)	Manual pressure, cautery, suture, adjuvant hemostat(s)	Manual pressure, cautery, suture, adjuvant hemostat(s)	Manual pressure, cautery, suture, staples, tissue repair	Manual pressure, cautery, suture, staples, tissue repair
Maximum Expected ACS-ATLS Shock Risk Class	1	1	1	2	3	4
Hemostasis	Yes	No	No	No	No	No

In cases where the target bleeding site is still bleeding at the 3 minute or 6 minute assessment time points, repeat application of the randomized hemostat will be performed.

In cases where hemostasis is not achieved by 10 minutes, the Investigator may use whatever means necessary in order to control bleeding, except for any hemostatic products containing thrombin or aprotinin (Thrombin-JMI, Evithrom, Floseal, Tisseel, Evicel, Tachosil, Evarrest). Recothrom should not be used in subjects randomized to receive HEMOBLAST™, but may be used in subjects randomized to the G+T arm.

In any case where hemostasis is initially achieved but bleeding recurs prior to subject closure, the event will be documented and treated as an adverse event, and the time of observation of the re-bleed will be recorded.

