Verbal Descriptor	None	Minimal	Mild	Moderate	Severe; not immediately life-threatening	Extreme; immediately life-threatening
Visual Descriptor	Dry	Oozing	Pooling	Flowing	Streaming	Gushing
Expected Intervention(s)	None	Manual pressure, cautery, adjuvant hemostat(s)	Manual pressure, cautery, suture, adjuvant hemostat(s)	Manual pressure, cautery, suture, adjuvant hemostat(s)	Manual pressure, cautery, suture, staples, tissue repair	Manual pressure, cautery, suture, staples, tissue repair
Maximum Expected ACS-ATLS² Shock Risk Class	1	1	1	2	3	4

¹ ACS-ATLS Shock Risk Class: 1 – involves up to 15% of blood volume; typically no change in vital signs and fluid resuscitation is not usually necessary. Class 2 – involves 15-30% of total blood volume; patient is often tachycardic with a narrowing of the difference between the systolic and diastolic blood pressures; the body attempts to compensate with peripheral vasoconstriction; skin may start to look pale and be cool to the touch; volume resuscitation with crystalloids is all that is typically required; blood transfusion is not typically required. Class 3 – involves loss of 30-40% of circulating blood volume; patient’s blood pressure drops; heart rate increases, peripheral hypoperfusion worsens; fluid resuscitation with crystalloid and blood transfusion are usually necessary. Class 4 – involves loss of > 40% of circulating blood volume; the limit of the body’s compensation is reached and aggressive resuscitation is required to prevent death.

The SBSS will be used to determine the intraoperative eligibility (described further in Section 5.5.1.3) as well as hemostatic success (described further in Section 6.4.3). Use of the SBSS will ensure consistent enrollment of TBSs of similar bleeding severities and help ensure subject safety by excluding those who have severe bleeding.

Investigators will be trained and tested on the SBSS prior to their enrollment of any subjects into the clinical investigation, as described further in Appendix D.

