6.4.5 Intraoperative Data Collection

The following data will be recorded on the Intraoperative CRF:

- Surgical procedure(s);
- Preparation times for each device;
- Description of TBS;
 - Location,
 - Tissue type,
 - Conventional means for hemostasis (pressure, suture, cautery, etc.),
- Confirmation of intraoperative eligibility criteria;
- Approximate dimensions of target bleeding site;
- SBSS score at baseline and each evaluation time point (3, 6, and/or 10 minutes) until hemostasis is achieved;
- Randomization;
 - Randomization envelope number,
 - Time of randomization,
 - Treatment arm and device lot/batch number data,
- Hemostat application;
 - Application amount
 - HEMOBLAST™ application amount will be approximated by indicating the amount of powder left in the bellows after application
 - G+T application amount will be documented by approximating the dimensions of Surgifoam sponge applied
- Rescue treatment(s), if any;
- Use of other hemostatic agent(s), if any;
- Skin open and skin closure times;
- Intraoperative administration of blood products;
- Total intraoperative estimated blood loss;
- Incidence of any device deficiencies; and

- Incidence of any complications or adverse events.

The Concomitant Medication, Adverse Event, and Device Deficiency CRFs will be completed as applicable.

Table 7 below shows a timeline of intraoperative procedures.

Table 7. Timeline for Intraoperative Procedures*

Time Point (Minutes:Seconds)	Study Procedures or Assessments
Prior to 00:00	
 • Prepare both hemostatic devices and record time of preparation • Identify Target Bleeding Site (TBS) • Assign SBSS score • Perform randomization (unless lead-in subject)
00:00	
 • Start stop-watch • Apply HEMOBLAST™ or G+T
03:00	
 • Assign SBSS score 
If SBSS = 0
 
 • Intraoperative efficacy evaluation completed 
If SBSS is NOT 0
 
 • Re-apply HEMOBLAST™ or G+T
06:00	
 • Assign SBSS score 
If SBSS = 0
 
 • Intraoperative efficacy evaluation completed 
If SBSS is NOT 0
 
 • Re-apply HEMOBLAST™ or G+T

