12.2.1 Analysis Populations

Safety analyses will be performed on the Full Analysis Population, defined as all subjects who were randomized into the study and received study intervention and all lead-in subjects. Efficacy analyses will be conducted on the time to hemostasis (TTH) Analysis Population, defined as all subjects who were randomized, received study intervention, and had a TTH assessment recorded regardless of whether the measurement was censored (defined as the use of an additional hemostatic product or surgical rescue prior to the end of observation time, or failing to achieve and maintain complete hemostasis prior to the end of observation time). Data summaries will be based on the intervention received, regardless of which intervention was randomly assigned.

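### The 3- and 6-minute re-application rule has no upper SBSS limit and conflicts with the protocol's own HEMOBLAST contraindication and instructions for use

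*Protocol*

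**What the plan says.** **Re-application.** Protocol 6.4.2: "Reapplication of the randomized hemostat will be performed at the 3 minute and 6 minute evaluation time points, as described below". Protocol 6.4.3: if the site is "still bleeding at the 3 minute or 6 minute assessment time points, repeat application of the randomized hemostat will be performed". Table 7 (Section 6.4.5) gives the trigger at 03:00 and 06:00 as "If SBSS is NOT 0" and the action as "Re-apply HEMOBLAST™ or G+T". SAP 8.1 repeats the 6.4.3 rule. Table 6 counts every score from 1 to 5 as failure of hemostasis.

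**Limits on use.** Among the HEMOBLAST contraindications in 6.4.2: "Do not use HEMOBLAST™ Bellows for treatment of severe or brisk bleeding". Step 7 of the application instructions in the same section offers either a repeat or another hemostasis method when bleeding continues. Section 3.5 requires strict adherence to the instructions for use. Section 4.3 gives as a goal that the hemostat not be used on severe bleeding. Tables 2, 3 and 6 list adjuvant hemostats among the expected interventions for SBSS 1 to 3, but not for 4 or 5.

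**Rescue.** Section 6.4.3: "In cases where hemostasis is not achieved by 10 minutes, the Investigator may use whatever means necessary in order to control bleeding", with certain products excluded. Table 7 shows rescue only at 10:00. Yet the definition of censoring in 12.2.1 includes "the use of an additional hemostatic product or surgical rescue prior to the end of observation time", and the success definition in Table 8 excludes subjects given an additional product or surgical rescue.

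**The concern.** Eligibility requires SBSS 1 to 3, but that is checked once, before treatment. The scale used at 3 and 6 minutes runs from 0 to 5, and the action rule divides it only into zero and not zero. An investigator who scores a HEMOBLAST-treated site 4 at 3:00 is told by three parts of the protocol to re-apply and by the contraindication not to use the product.

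This matters in two ways. First, it is a safety conflict, because a stated rule contradicts a stated contraindication. Second, sites may resolve it differently, and the choice made at 3 minutes can decide whether the subject counts as a success on the primary endpoint.

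**Working it through.** No figure in the plan bears on this point. For completeness, the stated 80.1% power was rechecked with a two-look calculation (88% in both arms, 267 and 133 subjects, 10-point margin, interim at 160 and 80, Table 9 boundaries). It gives 80.0% with the futility boundary applied and 81.4% with it ignored. The design arithmetic is not in question here.

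**Step 1: what each instruction requires if a HEMOBLAST site scores 4 or 5 at 3:00 or 6:00**

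| Source | Instruction |
|---|---|
| Protocol 6.4.2, general text | Re-apply at both time points |
| Protocol 6.4.3; SAP 8.1 | Re-apply if still bleeding |
| Table 7 | Re-apply if the score is not 0 |
| 6.4.2, application step 7 | Repeat, or use another method |
| 6.4.2, contraindications | Do not use for severe or brisk bleeding |
| 3.5 | Follow the instructions for use strictly |
| 4.3, stated goal | Hemostat not for severe bleeding |
| Tables 2 and 6 | No adjuvant hemostat among expected interventions |

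The first three rows are mandatory and have no ceiling. Step 7 makes repetition optional. The contraindication and the goal point the other way, and SBSS 4 carries the contraindication's own word, severe. The last row describes expected practice and is not a prohibition, so it is in tension with the rule but does not contradict it.

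**Step 2: the G+T arm.** The contraindication and step 7 concern HEMOBLAST. G+T is applied under its own instructions, which are not in the documents. For G+T only the Section 4.3 goal and the SBSS table remain.

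**Step 3: consequence for the primary endpoint.** Table 8 requires SBSS 0 achieved and maintained within 6 minutes without an additional product or surgical rescue. Section 12.2.2 makes values censored before 6 minutes failures. Because the timeline itself calls for re-application, I read the additional product as something other than the assigned hemostat.

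- Score 4 or 5 at 3:00, re-applied, score 0 at 6:00 and maintained, no rescue: primary success.
- Score 4 or 5 at 3:00, additional product or surgical rescue before 6:00: primary failure.
- Score 4 or 5 at 6:00: primary failure whatever is done next.

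The 3-minute endpoint is a failure in the first two cases. The primary endpoint is therefore sensitive to handling at 3 minutes, not at 6.

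**Step 4: scale.** At full size, reclassifying one subject moves the unadjusted success proportion by 1/267 = 0.37 percentage points in the HEMOBLAST arm, or 1/133 = 0.75 points in the G+T arm, against a 10-point margin. The number of such subjects cannot be derived. If 0.5% to 2% of 400 worsened to SBSS 4 or 5, that would be 2 to 8 subjects, but this range is an assumption with no basis in the documents.

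**The case against.** The best answer is that the protocol already leaves the investigator room. Application step 7 permits another method, and 6.4.2 and 3.5 bind HEMOBLAST use to its instructions, so re-application could be read as subject to them. Section 16.5 waives prior sponsor approval for changes that reduce overt risks and directs the investigator to act as medically sound in an emergency. The censoring definition, the success definition and the rescue field on the Intraoperative CRF all expect that rescue may occur, and nothing forbids other measures before 10 minutes.

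Much of this stands. A reader might infer that other means are withheld until 10 minutes. The text does not say so: it gives express permission at 10 minutes and foresees earlier rescue elsewhere. A reader might also infer that the two arms would be handled differently because only the HEMOBLAST contraindication is printed. That cannot be shown without the G+T labeling. Finally, the sentence in 4.3 that begins "Use of the SBSS will ensure consistent enrollment of TBSs of similar bleeding severities and help ensure subject safety by excluding those who have severe" concerns entry, so it is weak support for a rule about re-treatment.

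None of this removes the conflict. Step 7 is one more instruction that disagrees with Table 7. The analysis definitions classify outcomes and do not authorize actions. Section 16.5 works only as a departure from the plan, and Table 11 requires emergency deviations to be reported within 24 hours. An investigator should not have to depart from the plan in order to observe a contraindication that the plan itself prints.

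**Conclusion.** The point holds as a contradiction between written instructions. The re-application rule in 6.4.2, 6.4.3, Table 7 and SAP 8.1 covers every non-zero SBSS. It conflicts with the HEMOBLAST contraindication, with application step 7, with the strict-adherence requirement in 3.5 and with the goal in 4.3, and it is in tension with the SBSS table. For G+T it rests on 4.3 and the SBSS table alone. It deserves correction because it touches safety and is cheap to remove, not because of any effect on power.

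Its size is unknown, since no rate of worsening to SBSS 4 or 5 is given. A reader might infer that subjects who leave the timed sequence are already primary failures, or should be counted as such from the moment they worsen. The documents do not support this at 3 minutes: a site scored 4 at 3:00 and 0 at 6:00 without rescue is a success under Table 8. The conclusion assumes that Severe in the SBSS and severe in the contraindication mean the same thing, which the shared wording suggests but the protocol does not state.

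**What to change.** Reconcile 6.4.2 (the re-application sentence, step 7 and the contraindication), 6.4.3, Table 7 and SAP 8.1 with the goal in 4.3 and the earlier rescue foreseen in 12.2.1. State the 3- and 6-minute instruction by SBSS level, in the same terms in the protocol text, Table 7 and the SAP. Which clinical action applies at each level, in either arm, is for the sponsor and its medical experts.

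State that following the reconciled instruction is not a protocol deviation. Keep the existing analysis rule: these subjects stay in the TTH Population; those given an additional hemostatic product or surgical rescue before 6 minutes are primary failures under Table 8, 12.2.1 and 12.2.2; those not rescued are classified by the 6-minute SBSS as now defined.

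The cost is a few sentences, one table and the matching SAP paragraph. It needs no added subjects or procedures, and it leaves the endpoint definition and the planned sample size unchanged. If the chosen instruction leads to rescue at 3 minutes in some cases, those subjects lose the chance of a 6-minute success. The sponsor should accept that knowingly, although its frequency cannot be estimated from the documents.
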